2.4 Conflict of Interest for the SO

The SO has no direct involvement with the study investigators or intervention, and will sign a Conflict of Interest Statement which includes current affiliations, if any, with pharmaceutical and biotechnology companies (e.g., stockholder, consultant), and any other relationship that could be perceived as a conflict of interest related to the study and / or associated with commercial interests pertinent to study objectives.

2.5 Protection of Confidentiality

Data will be presented in a blinded manner in the open report for the SO, data and discussion are confidential. Participant identities will not be known to the SO.

2.6 SO Responsibilities

It is the responsibility of the SO to:

- Review the research protocol, informed consent documents and plans for data safety and monitoring;
- Recommend participant recruitment be initiated after receipt of a satisfactory protocol;
- Evaluate the progress of the trial, including periodic assessments of data quality and timeliness, recruitment, accrual and retention, participant risk versus benefit, performance of the trial sites, and other factors that can affect study outcome;
- Consider factors external to the study when relevant information becomes available, such as scientific or therapeutic developments that may have an impact on the safety of the participants or the ethics of the trial;
- Review study performance, make recommendations and assist in the resolution of problems reported by the PIs;
- Protect the safety of the study participants;
- Report to NIA on the safety and progress of the trial;
- Make recommendations to the NIA and the PIs concerning continuation, termination or other modifications of the trial based on the observed beneficial or adverse effects of the treatment under study;
- Ensure the confidentiality of the study data and the results of monitoring; and,
- Assist the NIA by commenting on any problems with study conduct, enrollment, sample size and/or data collection.

4) Study Population

- a) We will enroll 32 dementia at-risk seniors over 2 years. Our sample size is not based on demonstrating clinical efficacy but to obtain preliminary data and feasibility to plan our RO1.
- b) General inclusion criteria:

- i) Adults aged 65 and older. The age criterion is intended to maximize observed rates of age related decline in executive function.
 - ii) At-risk for dementia defined as meeting cutscores on either the **MIS (≤ 6)³⁸ or AD-8 (≥ 1)³⁹** tests administered by telephone.
 - iii) Plan to be in area for next year or more.
 - iv) Able to speak English at a level sufficient to undergo our interventions and cognitive assessment battery.
 - v) Willing to complete an MRI (exclusions relevant to neuroimaging are described below). Given our small sample size and budget limits of the R21 format we wanted to maximize study and budgetary efficiency by enrolling participants who not only agree to the study interventions but also agree to undergo neuroimaging.
- c) General exclusion criteria (one or more criteria):
- i) **Presence of dementia** based on telephone interview, previous established physician diagnosis of dementia or dementia diagnosed by [name] at initial visit.
 - ii) **Serious chronic or acute illness** such as cancer (late stage, metastatic, or on active treatment), chronic pulmonary disease on ventilator or continuous oxygen therapy or active liver disease. Individuals with recent cardiovascular or cerebrovascular event (MI, PTCA, CABG, or stroke) will not be excluded if they meet above inclusion criteria. *Many of these chronic conditions are very common in older adults. Hence, mere presence of these conditions will not be used to exclude subjects if well controlled or of mild severity and if subjects are able to complete the interventions.*
 - iii) **Mobility limitations solely due to musculoskeletal or cardiovascular conditions that prevent participation in the intervention programs.** Prevalence of arthritis is ~60% in the Einstein Aging Study³⁵, so mere presence of disease will not be used to exclude subjects if they can complete the mobility tasks. Screening clinician will assess and document presence of musculoskeletal diseases.
 - iv) Any **medical condition or chronic medication use** (e.g., neuroleptics) in the judgment of the screening clinician that will compromise safety or affect cognitive functioning.
 - v) **Terminal illness** with life expectancy less than 12 months.
 - vi) **Progressive, degenerative neurologic disease** (e.g., Parkinson's disease or ALS) diagnosed by [name] and as per medical history that will restrict mobility and participation in interventions.
 - vii) **Severe auditory or visual loss:** Vision is screened using a Snellen chart by the psychological assistant. Also, the neurologist tests visual fields using confrontation perimetry and near vision using Jaeger test types. Significant loss of vision is defined as corrected vision (using reading glasses) less than 20/400 on the Snellen chart with both eyes and inability to read any test sentence on the Jaeger test card with both eyes. Hearing is initially evaluated as part of the screening telephone interview. Subjects who attend the clinic visit will be excluded only if they are unable to follow questions asked in a loud voice (even with hearing aid in place).
 - viii) **Active psychoses or psychiatric symptoms** (such as agitation) noted during the clinic visit that will prevent completion of study protocols. Past history of these symptoms or presence of psychiatric illness not used as exclusion criteria.
 - ix) **Either participation in competitive dancing or recreational dancing at a frequency >1/month in the past six months.** As seniors may dance at social events (but not at doses or frequency to have cognitive benefits), excluding all seniors who ever danced is not practical. We will examine all reports of participation in cognitive enhancement programs (as this covers a wide range of activities) to judge inclusion.
 - x) **Participation in other interventional study that overlaps with intervention period of this study.**
- d) Specific Neuroimaging considerations: Additional exclusions relevant to neuroimaging include the presence of any surgically implanted metallic devices, such as aneurysm clips or pacemakers that would be a safety contraindication for MRI. Subjects with large amounts of dental or surgical hardware in the head and neck will be excluded because magnetic susceptibility effects will lead to severe image artifacts in these subjects' images. Due to the confined space of the MRI magnet, subjects with a known history of claustrophobia will also be excluded as will subjects with weight >350lbs or waist circumference >55 inches. Conditions that may confound the association between neuroimaging

cognition and mobility (normal pressure hydrocephalus or severe head trauma) will be excluded from analyses. We estimate that the prevalence of these conditions is very low based on other aging studies. Additional incidental findings that may be seen with a low prevalence in the elderly may include vascular anomalies or tumors. All scans will be reviewed by board-certified neuroradiologists. Abnormal results will be communicated to [name] who will initiate follow-up with subjects and their physicians as has been our established procedure in other studies based in our center.

- e) Recruitment, enrollment, and participation of participants in this project are not limited by gender, skin color, racial/ethnic group, or economic status. We will monitor recruitment and retention patterns to ensure adequate representation of women and minorities.
- f) **Research material** obtained from human subjects will be the results of clinical and neuropsychological testing obtained from study assessments and telephone interviews. The subject and their primary care physician will be informed of all clinical results that are relevant to patient care. Phenotypic data will also include results of MRIs, questionnaires, and body composition tests.

5) Participant Recruitment

- a) To achieve our study aims 32 participants will be recruited at random from commercially available lists of Bronx and Westchester County residents over the two-year funding period. We will also recruit participants from the Montefiore Medical Center Geriatrics and primary care clinics that have over 20,000 visits by patients, age 65 and older. We have had experience using both the community and clinic sources to recruit over participants for various aging studies in the past 10 years. Once telephone contact is achieved and the interview is complete, we assume that there will be a 20% loss due to lack of interest in the study and failure to meet general eligibility requirements and an additional 10% failure on the cognitive instruments (MIS or AD-8). There is an additional 10% loss in the remaining sample due to failure to meet eligibility requirements. Using telephone based recruitment instruments enables us to minimize loss due to not meeting criteria on in-person assessments.

A concern is that there might be attrition between the enrollment and start of the intervention in this high-risk group. To minimize this possibility, we will institute a rolling admission policy that we have successfully used in our ongoing cognitive remediation study.¹¹⁴ A different dance is taught in each session. As soon as we have enrolled a pair into the dance group, they will start the dance program in the next available day. This modified rolling admission policy will help reduce delays between enrollment and the start of the dance intervention. In the walking group, the intervention is individualized though participants exercise in groups on the treadmill to simulate the social nature of dancing. Hence, participants randomized to the walking arm can join the walking program at any point during the 2-year study period. Participants randomized to the walking group will also start the program at the next available day.

6) Informed Consent

- a) The study interviewer will conduct the initial telephone-screening interview. Potential subjects will be invited for further in-person evaluations. Study evaluations, enrollment, and in-person interventions will be done at our research center. [name] and the research assistant will diagnose and exclude cases following clinical and neuropsychological testing.
- b) **Compensation** at \$10/session consistent with IRB guidelines will be provided to participants. An additional \$25 will be provided to participants for completing each MRI.

7) Risk/Benefit

- a) **Potential risks:** We do not expect any serious adverse events during these non-invasive tests and training programs of attention and executive function. Answering health questionnaires and mental state examinations involve minimal psychological, social, or other risks.
 - i) Dance classes will be taught by certified dance instructors (with experience teaching seniors) at varying levels of complexity and the progression during the intervention period will be gradual. Progression to new dances will take into account the balance challenge, cardiovascular demand, degree of flexibility, coordination and cognitive demand. The instructor will ensure that the programs will not be manipulated to mimic exercise training as in aerobic dance classes.

- ii) The treadmill training walking intervention protocol will be based on recommendations of the American College of Sports Medicine (ACSM)¹⁰⁶ and American Heart Association (AHA) for older adults. A gradual approach will be applied to increase exercise intensity in participants with a low baseline level of physical activity and who may be unfamiliar with treadmill walking. Pulse and blood pressure will be assessed before and after each session to assure that the values are not deviated by 10 or more from the values of initial assessment for pulse and systolic blood pressure. During exercise, participants are monitored with the subjective Borg scale⁶⁸ every 5 minutes and heart rate is tracked by a physical therapist. Participants are encouraged to increase the training velocity if the subjective rating of exercise intensity is low (fairly light, Borg score <12). The treadmill speed will be reduced or exercise aborted if there are any untoward symptoms such as cardiovascular symptoms or excessive fatigue. Heart rate will be measured during the break between training periods and the second period will only be initiated after the value is below the 70% of estimated maximum heart rate.¹⁰⁶ Similar procedures will also be followed in the dance intervention group.

Since there are no significant risks associated with the procedures, this study is justified because useful new scientific knowledge will be obtained.

- b) **Protection against risk:** The research staff and investigators will be present during all testing. All questionnaire completion will be done at a slow enough pace so as not to tire individuals. If subjects express physical or mental tiredness or discomfort during any of the assessments or training procedures, the procedure will be terminated immediately. Drs. [name], [name] or the supervising investigator for each arm will be available onsite or by cellular telephone at all times to address any safety concerns or clinical issues during the interventions.

- i) **Fall safety:** Recent dance interventions using similar protocols in cognitively healthy and impaired participants report no or low rate of falls during dance sessions.^{34, 107} The rate of falls was <1% among 5,500 participants from 11 diverse physical activity interventions participating in a trans NIH collaborative known as the Behavior Change Consortium.¹⁰⁸ A Cochrane review of interventions to promote physical activity reported that of the 8 physical exercise trials with information on adverse events, fall rates were only significantly different from controls in 1 out of these 8 studies.¹⁰⁹ Another Cochrane review that addressed the role of exercise programs (mostly walking but no dancing interventions) for people with dementia concluded that exercise was not harmful though the cognitive benefits were not proven.¹¹⁰

Despite the low fall rate in these previous reviews, we take safety seriously, and have instituted a number of procedures to minimize fall risk in our pilot trial. Both the dance and walking groups are closely supervised. The groups are small so that instructors can pay attention to the participants, and intervene if balance problems are noted during the session. Participants will be instructed to wear sports shoes with good grip soles. Footwear and clothing will be inspected by the instructors prior to the start of sessions to ensure that they are appropriate for both intervention activities. Wooden complaint flooring used in our dance space is associated with lower risk of fall injury than hard flooring, though not as low as carpeted wooden flooring.^{111, 112} However, carpets were reported to be associated with falls in a Cochrane review of studies.¹¹³ It would not be practical to have safety harnesses on participants in the dance group, and this has not been the practice in the multiple previous dance intervention studies. Participants in both groups will be frequently asked about their comfort/discomfort levels. The intervention will be stopped if participants report any unsteadiness or balance problems, and will be examined by the study clinician. Our research center is located within a hospital complex, and referral to primary care physician or emergency room will be done as required. Our safety experience in this pilot trial will inform the design and conduct of our full scale RO1.

- ii) **Musculoskeletal injuries:** Given the sedentary nature of our participants (new criterion included as suggested by reviewer), musculoskeletal symptoms or injuries may occur. Previous studies suggest that though musculoskeletal complaints are common in physical activity interventions, the majority of these issues are mild in nature.¹⁰⁸ Both the dance and walking groups are closely supervised. The groups are small so that instructors can pay attention to the participants. Participants are frequently asked about their comfort/discomfort levels including the Borg scale. The intervention will be stopped

if participants report any discomfort, and will be examined by the study clinician. Our research center is located within a hospital complex, and referral to primary care physician or emergency room will be done depending on the severity of the problem.

- iii) **Neuroimaging results:** [name] will be immediately contacted in the event that an acute imaging finding requiring immediate action is discovered. She will review the reports of all MRI studies. Participants with normal studies will receive a letter to this effect. In the event that a non-urgent significant abnormality is discovered, [name] will contact the participant by telephone to discuss the findings and advise that appropriate PMD follow-up be obtained. A follow-up letter summarizing the discussion will be sent to the participant. If the participant wishes, the report will be sent to the PMD.
- iv) **MRI Safety program:** A comprehensive MRI safety program is in place including secure access to the MRI suite and ongoing surveillance for effectiveness of the safety program. A board certified subspecialty neuroradiologist will review each MRI scan for pathology and confirm that there are no clinically significant findings for any of the participants. All data are archived in the Picture Archival and Communication System (PACS) and if needed can be archived in DVD-R media and stored in a locked cabinet.

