Aim 2: Explore functional and structural neuroplasticity for cognitive benefits of social dancing in seniors at risk for dementia. We will explore neuroplasticity in functional activation/deactivation and structural connectivity patterns as a function of social dancing (pre-post intervention). We will use **functional Magnetic Resonance Imaging (fMRI)** to investigate neuroplasticity in functional activation/deactivation patterns with our validated 'imagined WWT' task³²- as well as with DSST and Flanker tests, which are responsive to physical interventions.²⁵ *We predict that compared to walking, dancing will result in greater intervention-related changes in functional activation of supplementary motor, anterior cingulate and prefrontal regions during imagined WWT, DSST and Flanker tests.*

To investigate neuroplasticity in structural connectivity patterns, we will use **diffusion-weighted imaging**, which are responsive to social dancing and physical interventions.^{33, 34} We predict that compared to walking, dancing will result in greater intervention-related changes in structural connectivity patterns, including fornix and cingulum.

Social dancing appeals to older adults, has intrinsic value, is enjoyable, and has high potential for sustainability. This R21 proposal is novel and high risk, but will provide the evidence base to develop a

definitive full-scale RCT to support or refute prescription of social dancing to prevent cognitive decline in older adults at high risk of AD and related dementias.

2) Study Design

Overview and Design. We propose a pilot single blind RCT of social dancing versus walking in 32 dementia at-risk seniors (16/group). For Aim 1, outcome is change in EF composite score measured with a comprehensive battery of conventional (DSST), computerized (Flanker test) and cognitive-motor (WWT) EF tests assessed at baseline, month 2, month 4, month 6 (immediate post-intervention), and 3 months post-intervention to derive trajectories to inform design of future R01. Feasibility is assessed through metrics described in Table 1. For Aim 2, outcome is neuroplasticity measured using our *validated fMRI iWWT protocol, DSST and Flanker Tests, and white matter integrity*.

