- d) **OUTCOMES Aim 1 (Cognition):** As EF includes multiple cognitive processes; a single test is not sufficient. We will examine a **composite EF score** by summing standardized scores on the 3 tests. Composite cognitive scores were used in many RCTs.²¹⁻²³ We will also compare trajectories in individual tests to gain insights into study design of our full-scale RO1. Study outcomes will be assessed at baseline, month 2, month 4, post-intervention (end of month 6), and 3 months post-intervention (month 9).

- i) **Digit Symbol Substitution test (DSST)** is a timed test that assesses speed of processing, visuo-spatial attention and EF. DSST predicts cognitive (dementia) and non-cognitive outcomes (falls). DSST is amenable to exercise.⁶⁹
- ii) **Flanker Test** is in the NIH toolbox.^{19, 20} It measures attention and inhibitory control. The Flanker test was used to demonstrate exercise effects on EF.^{8, 70}
- iii) **Walking While Talking test (WWT)** is an EF-dependent everyday behavior measure developed by our group.^{29, 30} Dual-tasking assessed by WWT is a defined facet of EF,^{36, 71} and associated with increased prefrontal activation.⁷² Participants walk on an instrumented walkway for 2 trials reciting alternate letters of the alphabet.⁷³ See our published papers for WWT procedures.^{28-30, 72-74} WWT has excellent test-retest and inter-rater reliability.²⁸⁻³⁰

Blinding: While double-blinding both subjects and testers is not feasible, the following steps (besides randomization) are included: A. Selection bias reduced by concealing treatment allocation until subject enrolled.⁷⁵ B. Outcome is an objective endpoint and not subjective reports.⁷⁵ C. Dance and walking groups meet non-overlapping times. D. Each aspect of the RCT is supervised independently: interventions ([name]), assessments ([name]) and imaging ([name]). E. Participants/staff instructed not to disclose group assignment or interventions.

Learning effects: We will utilize 4 complementary approaches to attenuate practice effects⁷⁶: (1) Practice pre-baseline to reduce task familiarity effects; (2) Item-specific driven improvements minimized by using tasks with multiple similar items and standardized encoding; (3) We developed alternate forms for the WWT task,⁷⁴ and alternate forms of the DSST are available; and (4) use of control group.

- e) **OUTCOME Aim 1 (Feasibility):** Metrics below will identify barriers and refine design of our full scale RCT.⁷⁷

Metric	Measurement	Comments

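### The visual-loss exclusion requires failure on both the distance and the near-reading test, so a person who can read no near print may enter a trial whose outcome relies on visual tests

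*Combined protocol and SAP*

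**What the plan says.** Section 4 c) vii sets the visual exclusion in two limbs, distance and near, joined in one sentence. Visual loss is significant when corrected vision is "less than 20/400 on the Snellen chart with both eyes and inability to read any test sentence on the Jaeger test card", the near limb again applying to both eyes. The list as a whole is headed "General exclusion criteria (one or more criteria", so any single item from i to x excludes. That heading says nothing about how the two limbs inside vii combine. The neurologist also tests visual fields, but no field result enters the definition.

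Section 2 d) builds the Aim 1 composite "by summing standardized scores on the 3 tests". It says the DSST "is a timed test that assesses speed of processing, visuo-spatial attention and EF". The study design overview lists "computerized (Flanker test) and cognitive-motor (WWT) EF tests" as the other two components. As described in section 2 d) iii, the WWT involves walking and reciting letters, with no reading of near print. Versions of the DSST and Flanker are repeated in the scanner for Aim 2 (section 2 f) i). Under Learning effects, the plan already provides for "Practice pre-baseline to reduce task familiarity effects".

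**The concern.** An eligibility rule should make sure that everyone randomized can produce a valid primary measurement. Elsewhere in section 4 it does. English must be good enough for the interventions and the test battery, and hearing is judged by whether the person can follow spoken questions. Vision is the exception: failing the near-reading test excludes nobody by itself.

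A participant who can read no near sentence cannot validly do the DSST, and probably cannot do the Flanker. Their scores on those components would sit at the floor at every visit, reflect eyesight rather than executive function, and be unable to respond to either intervention. Alternatively they would be missing, and the plan gives no rule for a composite with a missing component; section 8 c) answers missing data with contact persons and flexible scheduling. With 16 per arm, one such person is visible in the estimates. Those estimates matter because section 8 states that the purpose of the analysis is to inform a larger trial.

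**Working it through.** **The rule as written.** There are four combinations of the two limbs:

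| Distance (Snellen) | Near (Jaeger) | Excluded by vii? |
|---|---|---|
| below 20/400 | reads no sentence | yes |
| 20/400 or better | reads no sentence | no |
| below 20/400 | reads a sentence | no |
| 20/400 or better | reads a sentence | no |

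The second row is the gap.

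**Other criteria that might close it.** The eligibility text in sections 2 b) and 4 contains no other vision requirement. Item viii refers to completing study procedures, but only for psychiatric symptoms. Item iv lets the screening clinician exclude for medical conditions that bear on safety or cognition. It does not name vision or ability to do the tests.

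**Size if one such person is enrolled.** The documents give no figure for this, so the following inputs are assumptions:
- one affected participant among 32;
- a floor score k SD below the mean of the other 31, who have mean 0 and variance 1;
- standardisation by the baseline SD of all 32 (the plan names no reference SD);
- equal effects on the three tests.

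*Inflation of the SD of one affected test:* SD = sqrt[(31 + k²)/32 − (k/32)²].
- k = 2: sqrt(1.0938 − 0.0039) = 1.044; reciprocal 0.958, a shrinkage of 4.2%.
- k = 3: sqrt(1.2500 − 0.0088) = 1.114; reciprocal 0.898, a shrinkage of 10.2%.
- k = 4: sqrt(1.4688 − 0.0156) = 1.205; reciprocal 0.830, a shrinkage of 17.0%.

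*Carried to the sum of three tests:* multiply by 1/3 if only the DSST is affected, or by 2/3 if the Flanker is affected too.
- k = 2: 1.4% to 2.8%.
- k = 3: 3.4% to 6.8%.
- k = 4: 5.7% to 11.3%.

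*Dilution of that arm's mean change:* if the affected person's change on a test is zero, the arm mean is (15Δ + 0)/16 = 0.9375Δ, a loss of 1/16 = 6.25% on that test. On the composite this is 6.25%/3 = 2.1% to 2 × 6.25%/3 = 4.2%.

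The two effects differ in kind. The first is mostly a change of units, while the second is a real loss of signal in one arm.

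*If the scores are missing rather than at floor,* neither calculation applies. The participant would have no complete composite at any visit, and that arm would lose 1 of its 16 participants from the composite analysis.

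**The case against.** Several points against the concern stand.

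- **There is a discretionary backstop.** A reader might infer that nothing else could exclude such a person. That goes too far. Near vision is tested by the neurologist, eligibility is settled in person with the study clinician, and whether someone with this degree of visual loss can safely dance or use a treadmill is a judgment that item iv allows. Enrollment is permitted by the written rule, not expected.
- **Only the DSST is described as visual.** A reader might infer that two thirds of the composite would measure eyesight. For the Flanker this is inferred from its being computerized with congruent and incongruent trials; stimulus size is not given. The range therefore has to start at one test.
- **The per-test figures overstate the effect.** A reader might infer that one outlier shrinks every effect by 10%. That figure is for one affected test, while the outcome is a sum of three. Moreover, dividing one test by a larger SD rescales effect and residual alike, so that test's t-statistic does not change. On the composite, what remains is some shift of weight towards the WWT.
- **Non-completion would be seen.** The feasibility table already tracks completion and tester feedback. That would reveal the problem, but only after the person had been randomized.
- **The case is rare and the trial is a pilot.** Its sample size is expressly not set to show efficacy.

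None of this removes the gap in the wording of vii, and discretion is not a rule that can be applied the same way to every candidate.

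**Conclusion.** The point holds as a minor one. Taken at its plain meaning, criterion vii does not exclude a person who can read no near sentence but sees 20/400 or slightly better, and the only other route to exclusion is clinical discretion. Such a participant would give floor or missing scores on one component of the EF composite (DSST) or two (DSST and Flanker), and on the in-scanner versions.

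Conditional on one such participant at 3 SD below the mean, with pooled baseline standardisation and equal effects across tests, the summed composite effect shrinks by about 3% to 7%, and the affected arm's mean change is diluted by about 2% to 4%. The documents give no prevalence, so the expected number among 32 cannot be computed; it should be small.

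A reader might infer that the comparison of dance with walking is biased. The documents do not support that. The rule is applied before randomization to all candidates alike, so which arm receives such a person is a matter of chance. The harm is added noise and attenuation.

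**What to change.** Add a functional check to the pre-baseline practice already planned under Learning effects: with usual correction, the participant must be able to read the DSST key and identify the Flanker stimuli. State that this takes place before randomization. Section 2 c) places randomization at the initial visit, and the plan does not say where the practice falls relative to it.

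Then reconcile the wording of criterion vii with the visual demands of the EF battery. Simply replacing the conjunction with *or* fits the problem poorly. It would exclude people with poor distance vision who can read near print, and it would still admit people who read only the largest near sentence and may not manage the DSST key. The functional check addresses the measurement problem directly.

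The cost is one checklist item, a short wording change, and possibly one or two more screen failures.
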